Participants will be randomized to the two treatment groups with matching placebos for drugs in the other arm, in equal proportions. Randomization will be stratified by site and MELD score. Random blocks of size 4 will be generated to ensure treatment assignments are balanced between the two treatment arms within each block. Both participants, coordinators, and investigators will be blinded to the randomization plans.

Statistical Analyses

The primary analyses of 90-day mortality will be performed in an Intention-to-Treat (ITT) framework using survival analysis. Specifically,

- (1) we will use all-cause mortality in the first 90-days as the primary outcome event of interest. We will compare the distributions of time to mortality between the two treatment arms. In the primary analysis, mortality event times greater than 90 days will be censored at the 90 days or at the time of liver transplant, whichever comes first. We will use the Logrank test to compare the survival functions of the two treatment groups. Cox regression analysis can be performed if it is necessary to control for the influences of unbalanced patient characteristics, such as MELD score, between the treatment groups. If evidence suggests a violation of the hazard function proportionality, we will conduct an analysis of the restricted mean survival time (RMST) of the first 90 days.
- (2) as a secondary analysis, we will compare transplant-free survival in the first 90 days of treatment initiation as between the two treatment arms, as done in other clinical trials. We will perform logrank test, Cox regression, and RMST analyses as appropriate.
- (3) we plan to conduct one interim analysis and one final analysis for this trial. The interim analysis will be conducted when **129** patients, half of the enrollment number, complete the 90-day follow-up. We use the group sequential method to control the type 1 error rate of the trial.
- (4) as another secondary analysis, we will examine the treatment effects in patients with baseline MELD scores ≤ 25 and > 25 by assessing the equality of treatment effects of the anakinra in high and low MELD groups, we will test the interaction between the intervention indicator and baseline MELD score in the Cox regression model.

Subject Participation Duration

180 days

Recruitment and Retention Plan

Sources of participants:

Identification of participants with severe AH requires collaboration with those physicians who manage these participants within the hospital and the emergency department. Almost 100% of participants are admitted to hospital based on the severity of their liver disease. Occasionally participants are seen in free-standing urgent care centers, free-standing emergency rooms or in office/clinic practices. Since the standard of care is to admit these participants for further evaluation to exclude infections as a precipitating cause of decompensated liver disease, most will ultimately be identified in a hospital setting. Letters will also be sent to referring MDs and referring hospitals.

Some sites in the current U01 have found that screening laboratory results for elevated AST and total bilirubin is a useful way to identify potential participants. In accordance with Institutional Review Board Policies, once identified the primary team caring for these participants must be contacted by the investigators and agree to ask the participant about their interest in participating in a clinical trial as part of the treatment of the underlying AH. Once the participant expresses willingness to be contacted the investigators may discuss details of the study and obtain informed consent prior to beginning treatment.

Management of barriers for recruitment:

Special conferences with medicine, ICU and ER staff will increase awareness of the trial, and its significance. Contact information for study personnel will be made available so that they can meet with participants and their family to educate them about AH and the trial. For those who live at a distance, travel costs will be budgeted in alignment with local practices for other trials.

Contingency plans:

Recruitment will be tracked with monthly review of expected versus actual enrollment. Screen fail rates will also be assessed. There will be direct communication between DCC-IU, NIAAA and study leadership with site-PI and staff to better understand the barriers for recruitment and develop/implement solutions. Best practices from high-performing sites will be shared with the under-performing sites. For continued failure, the site budgets will be cut, and funds redirected towards supporting enrollment at high performing sites after discussion with NIAAA project officer.

Retention plan:

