2. EXECUTIVE SUMMARY

Title of Trial

A multicenter, randomized, double blinded, placebo-controlled clinical trial of Anakinra (plus zinc) or prednisone in participants with severe alcoholic hepatitis by the AlcHepNet Consortium.

Name of Active Ingredient(s)

- a. Anakinra
- b. Prednisone
- c. Zinc-Sulfate

Pharmacological Class of the Drugs

- a. Anakinra is immunological agent, an inhibitor of the Interleukin-1 receptor (IL-1).
- b. Prednisone is an adrenal glucocorticoid.
- c. Zinc-sulfate is a nutritional supplement.

Indication

Severe alcoholic hepatitis.

Study Type

Phase 2B multicenter randomized, 2-arm, double blinded, placebo controlled clinical trial.

Investigational Sites

Indiana University, Mayo Clinic, Virginia Commonwealth University, Cleveland Clinic Foundation, University of Louisville, Beth Israel Deaconess Medical Center, University of Pittsburgh Medical Center, and University of Texas Southwestern Medical Center

Planned Number of Participants

Approximately 258 participants will be randomized in a 1:1 ratio into 1 of 2 treatment arms (129 participants per arm): (1) Prednisone + Placebo for Anakinra/Zinc (2) Anakinra + Zinc + Placebo for Prednisone.

Objectives

This multicenter, randomized, double blinded, placebo-controlled clinical trial is focused on novel treatments for severe alcoholic hepatitis (AH), a life-threatening stage of alcoholic liver injury that has a short-term mortality rate much higher than that of other liver diseases.

The primary objective of the study is to determine the clinical efficacy and safety of Anakinra (plus zinc) compared to the current standard medical treatment consisting of prednisone in participants with clinically severe AH. Key secondary objectives broadly are as follows: (a) to evaluate the use of biomarkers to assess disease severity and treatment response; and (b) to develop novel endpoints to overcome the limitations of current assessment strategies for severe AH.

Overview of Study Design and Conduct

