The proposed study is a Phase 2b, multicenter, prospective, randomized, 2-arm, double blinded, placebo-controlled clinical trial to assess the efficacy of Anakinra, an interleukin (IL)-1 receptor antagonist plus zinc compared to prednisone for the treatment of severe AH (Model for End Stage Liver Disease (MELD) score ≥ 20). All participants will receive standard care for treatment of severe AH as described in recent guidelines endorsed by American Association for the Study of Liver Diseases (AASLD) and American Gastroenterological Association (AGA). The study will be conducted at 8 clinical sites across the United States selected by the National Institute of Alcoholic Abuse and Alcoholism (NIAAA) and will be supported by a Data Coordinating Center at Indiana University (DCC-IU). The biorepository will be managed by University of Massachusetts.

The study will be conducted according to Good Clinical Practice (GCP) and in compliance with local, state, and federal regulatory requirements. Adverse events during the course of the trial will be identified, recorded, assessed for causality, and reported in accordance with FDA guidance. In addition to general assessment, we will specifically focus on (1) rates and types of infection as well as their severity, (2) potential development of drug-induced liver injury, (3) injection site reactions, and (4) hematological adverse events.

This study will be approved by an appropriately convened single IRB, Western Institutional Review Board (WIRB), and will be monitored by an NIAAA appointed Data and Safety Monitoring Board (DSMB). We will conduct this study under an Investigational New Drug (IND) application from the United States Food and Drug Administration (FDA).

It is anticipated that a centrally located investigational pharmacy located at Indiana University will dispense the study medications to all participating sites under close coordination from the DCC-IU. Anakinra plus zinc, prednisone and matching placebos will be provided by the study to the participants.

Interventions to be tested

[figure not shown]

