6.5 Randomization

6.5.1 Method of Assigning Participants to Treatment Groups

The trial will be conducted in a double-blind, placebo-controlled manner. Participants will be randomized to the two treatment groups in equal proportions. The randomization plan will be stratified by site and MELD score. Blocks of size 4 will be generated randomly based on a predefined randomization code generated by the AlcHepNet IU data coordinating unit (DCC- IU). Both participants and investigators will be blinded to the randomization plans.

The investigator or designee will be required to register the participant into the REDCap system (AlcHepNet’s data management system) and will provide participant data to properly randomize and allocate the participant to treatment. A randomization number will be assigned and study medication dispensing information (e.g., arm assignment) will be provided.

In the unlikely event of a system failure, the randomization will occur outside of REDCap according to the back-up emergency plan detailed in the Manual of Operations. IU DCC will maintain at all times a current, off-line randomization list and will be able to act as the Emergency Support team until the system is restored to its full capacity.

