6.6.1 Treatment and holding/stopping rules for infection and sepsis

Leukocytosis is common in AH and may be further exacerbated by administration of prednisone. Such iatrogenic rise in leukocytosis may alarm participant care teams who are blinded to the treatment arm and may raise concern for development of infection or sepsis.

While many AH participants may develop the systemic inflammatory response syndrome (SIRS) (defined as two or more abnormalities in temperature, increased heart rate, respiration, or white blood cell count), SIRS may not always be indicative of infection in participants with AH and may be reflective of the dysregulated inflammatory state with AH.

Drug Holding Rules (Day 0-Day 30):

If one of the following criteria met, the study drugs should be held for 3 days:

1. Documented Infection
 - Pneumonia defined as new infiltrate by CXR or chest CT scan
 - Positive cultures (blood, ascites) for bacteria or fungus
 - Positive fungal cultures in urine ($> 50,000$ colonies/ml)
 - CNS infection defined as positive cultures or WBC > 5 in CSF
 - Severe soft tissue or bone infections including clinical diagnosis of cellulitis
2. SIRS (defined as two or more abnormalities in temperature, increased heartrate, respiration, or white blood cell count) with increase in SOFA score ≥ 2 points.

Participants will be reassessed on 3rd day to determine if study drugs could be resumed or should be stopped.

Drug Stopping rules (Day 0-Day 30):

Participants will be reassessed on third day of the study drugs hold: If infection clears and participant stabilizes, study drugs will be resumed.

1. For participants with documented infection: If infection is responsive to antibiotics and participant is stabilized or improved, study drugs may be resumed at the discretion of the clinical care team. If there is no improvement after 3 days, study drugs will be stopped.
2. For participants meeting only SOFA+SIRS criteria for stopping: if cultures of urine, blood, ascites, stool (including C. diff) are negative and CXR is unchanged, study drugs may be resumed at the discretion of the clinical care team.
3. If the participant has a second hold of study drugs due to infection/SOFA+SIRS criteria, study drugs will be stopped.
4. Participants in either arm who have a Lille score of >0.45 on day 7 will stop bottle 1 (prednisone/ placebo) and will continue with bottle 2 (zinc/zinc placebo.)

Drug stopping Rules (Day 0-Day 30):

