6.6.2 Unscheduled, Emergency Unblinding

6.6.2.1 Rules for unblinding participants for leukocytosis and concern for infection/sepsis (Day 0-Day 30):

In this placebo-controlled, blinded and randomized trial, Principal Investigators, enrolled participants, and any study team member who will/is interpreting data will remain blinded.

1. If the participant develops leukocytosis $> 30 \times 10^9/\text{L}$ or $\text{WBC} > 30,000/\text{mm}^3$, the clinical care team may request unblinding if the team believes that knowing the treatment would impact care decisions such as starting antibiotics.
2. If the participant develops hypotension (systolic BP < 90) and/or requires transfer to an ICU, the clinical care team may request unblinding if the team believes that knowing the treatment would impact care decisions such as administration of pressors, fluids or other supportive therapy.
3. If the participant develops any other serious adverse event that is in the opinion of the investigator, probably related to one of the study drugs, the clinical care team may request unblinding if it would impact care decisions.

Who to unblind?

- Only sub-investigator
- Clinical care team
- DCC contact

Unblinding procedure:

1. Each site will designate a sub-investigator who can be contacted if the participant care team has concerns about rising leukocytosis
2. The contacted sub-investigator will communicate with IU DCC to unblind the participant then inform participant care team of the study drug/s participant is receiving
3. IU DCC will build this into the database system and keep track of unblinded participants
4. The decision to begin antibiotics for possible infection is left to the judgment of the clinical care team.

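### A single block size of 4, printed in the protocol, makes some assignments foreseeable to site staff who know earlier ones: a modest allocation-concealment weakness

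*Combined protocol and SAP*

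**What the plan says.** **Block size.** The Executive Summary (Group Assignment) says: "Random blocks of size 4 will be generated to ensure treatment assignments are balanced between the two treatment arms within each block". Section 6.5.1 repeats it: "Blocks of size 4 will be generated randomly based on a predefined randomization code generated by the AlcHepNet IU data coordinating unit". In both places the randomness concerns how the blocks are generated. No second size is named, and nothing says the size is withheld from sites.

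**Strata and numbers.** "The randomization plan will be stratified by site and MELD score". The MELD cut-point used for randomization is not given; the split at 25 appears only for a subgroup analysis. On numbers: "Approximately 258 participants will be randomized in a 1:1 ratio into 1 of 2 treatment arms", and "The study will be conducted at 8 clinical sites across the United States".

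**Who is blinded.** Group Assignment keeps participants, coordinators and investigators blind to the randomization plans. Section 6.6.2 keeps principal investigators blind.

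**Who may know assignments.** Section 6.6 makes the site pharmacist and site pharmacy staff unblinded, although section 6.1.2 says the pharmacy cannot tell the treatments apart. Section 6.6.2 allows the care team to ask for unblinding after WBC above 30,000, systolic pressure below 90 and/or ICU transfer, or a serious event probably related to study drug. The procedure is: "The contacted sub-investigator will communicate with IU DCC to unblind the participant then inform participant care team".

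**Who recruits.** Section 5.3.2 has the primary treating team agree to raise the trial with a patient before the investigators approach. No text separates those who have learned an assignment from later screening, referral or enrolment.

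**The concern.** Blinding to the randomization plans loses some force when the protocol prints the feature that makes a sequence guessable. In a 1:1 block of 4, two known assignments to the same arm fix all the others in the block. A person who knows the block size, the order of enrolment in the stratum and some earlier assignments can sometimes deduce the next one before a patient is approached or judged eligible.

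If that knowledge influenced who was enrolled, the arms could differ in prognosis. Intention-to-treat analysis does not guard against selection before randomization, and Cox adjustment deals only with measured covariates. The planning rates imply about 35 deaths (129 × (0.20 + 0.07) = 34.8), so a few selectively enrolled patients could matter. Exclusion criterion 20, on perceived inability to comply, leaves room for judgment at entry.

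**Working it through.** The plan gives no predictability figure, so there is none to reproduce.

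**Inputs.** Block size 4, ratio 1:1, 258 participants, 8 sites (Executive Summary; section 6.5.1). The share q of earlier assignments known to a recruiter is not in the documents and is assumed, with a range of 5% to 100%. Each earlier assignment is taken as known independently with probability q.

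**Certain assignments, blocks of 4.** There are 6 possible sequences.
- Positions 1 and 2 are never certain.
- Position 3 is certain if the first two are alike (2 of 6 sequences) and both are known: q²/3.
- The first three assignments always split 2:1. Position 4 is certain if the two like ones are known: q².
- Share certain = (q²/3 + q²)/4 = q²/3.

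**Correct guesses, choosing the likelier arm.**
- Position 1: 1/2.
- Position 2: 1/2 + q/6.
- Position 3: 1/2 + [1 − (1 − q)²]/6.
- Position 4: (1 − q)³/2 + 2q(1 − q)² + 2q²(1 − q) + q³.

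At q = 1 these are 0.500, 0.667, 0.667 and 1.000, with mean 0.708.

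| q (assumed) | certain | certain, of 258 | guessed correctly |
|---|---|---|---|
| 100% | 33.3% | 86 | 70.8% |
| 50% | 8.3% | 21.5 | 59.9% |
| 25% | 2.1% | 5.4 | 55.4% |
| 10% | 0.33% | 0.9 | 52.3% |
| 5% | 0.08% | 0.2 | 51.2% |

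Chance alone gives 50% correct.

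**Concealed mix of 4 and 6.** Take a stratum's first block, of size 6 (20 sequences), with all earlier assignments known.
- Three identical first assignments fix the remaining three: 2/20 × 3/6 = 5%.
- A 3:1 split after four, reached without three identical at the start, rules out size 4 and fixes the last two: 6/20 × 2/6 = 10%.
- Total: 15% of positions in that block.

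Later in a stratum the block boundaries become uncertain to the guesser. A simulation of 20,000 strata of 16, with both sizes equally likely, gives these overall figures:

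| q (assumed) | certain: fixed 4 | certain: mix of 4 and 6 | correct: fixed 4 | correct: mix of 4 and 6 |
|---|---|---|---|---|
| 100% | 33.3% | 6.1% | 70.8% | 68.3% |
| 25% | 2.1% | 0.05% | 55.4% | 54.8% |
| 10% | 0.33% | under 0.01% | 52.3% | 52.2% |

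**Pace.** 258/8 = 32.25 per site, or about 16 per stratum if MELD has two levels (an assumption). Over the 5 years in section 4.3 that is about 3.2 per stratum per year, so one block spans about 4/3.2 = 1.25 years, or 15 months.

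**The case against.** The trial is double-dummy, with identical capsules and manufacturer-supplied placebo syringes, and assignment runs through REDCap from a DCC code. Knowing every earlier assignment is not how the trial is meant to run. Unblinding is by request and only where it would change care. Section 6.6 adds discussion with the study physician and DSMB review of premature unblinding. At 5% to 10% known, fewer than one of 258 assignments is expected to be certain. Slow accrual makes it harder to track block positions. All of this stands, and it is why the point is modest.

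A reader might infer that the unblinding triggers are frequent in this population. The documents do not support that: they give no frequency for WBC above 30,000, systolic pressure below 90 or ICU transfer. Section 6.6.1 says only: "Leukocytosis is common in AH and may be further exacerbated by administration of prednisone". That concerns leukocytosis in general, and WBC above 30,000 is excluded at entry. Because the disease itself raises the count, it is also a weak clue to arm. Injection-site redness is listed for anakinra in more than 20% of participants, but both arms receive injections and no placebo rate is given.

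It is also fair to object that varying the block size hardly lowers the average guessing advantage. That stands too, and it is why the remedy needs a rule on who may recruit.

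The objection does not remove the route itself. The size is printed, pharmacy staff hold every assignment at their site, others may be told some, the treating team helps decide who is approached, and nothing separates these roles.

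**Conclusion.** The weakness is real but modest. With one known block size of 4, the share of assignments that are certain is q²/3: about 0.08%, 0.33% and 2.1% at an assumed 5%, 10% and 25% known, up to 33.3% if all are known.

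A reader might infer that a third of the assignments are foreseeable or that concealment has failed. The documents do not support this. The 33.3% and 70.8% figures are upper bounds that would need, for example, the pharmacy's full knowledge to reach recruiters, and section 6.6 requires pharmacy staff to be trained to keep the blind.

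The figures assume that assignments become known independently and before the next enrolment, and that the recruiter tracks order within the stratum. If knowledge clusters at one site, the share there would be higher than the average suggests. The sample-size calculation is not affected.

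**What to change.** 1. For blocks not yet started, draw block sizes at random (for example 4 and 6) and hold them only in a restricted DCC randomization file.
2. Replace the block-size sentences in the Executive Summary (Group Assignment) and section 6.5.1 with: permuted blocks of randomly varying size.
3. State in section 6.5.1 or 6.6 that site staff unblinded to any assignment take no part in later eligibility or enrolment decisions, and say whether this covers the treating team's first approach to patients.
4. Reconcile sections 6.1.2 and 6.6 on whether site pharmacy staff know the assignments.

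Item 1 mainly removes certainty; item 3 closes the route directly. The unblinding criteria themselves need no change for this purpose.

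**Cost.** A new REDCap list for future blocks, a few sentences of text, and some separation of roles at sites. The largest possible imbalance within a stratum rises from 2 to 3. Endpoint, sample size and analysis are unchanged.

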BP	blood pressure
BAS	bile acid sequestrants
BUN	blood urea nitrogen
CBC	complete blood count
CDCA	chenodeoxycholic acid
C.Diff	clostridium difficile
CFR	code of federal regulations
CLDQ	chronic liver disease questionnaire
CMP	complete metabolic panel
C _{max}	maximum concentration
CRA	clinical research associate
COVID-19	Coronavirus disease 2019
CRF	case report form
CT	computerized tomography
DCC	data coordinating center
DCA	deoxycholic acid
DCC-IU	data coordinating center-Indiana University
DILI	drug induced liver injury
dL	deciliter(s)
DSMB	data and safety monitoring board

ECG	electrocardiogram
ER	emergency room
FDA	Food and Drug Administration
FGF-19	fibroblast growth factor-19
FXR	farnesoid X receptor
GGT	gamma-glutamyltransferase
GMP	good manufacturing practice
GCP	good clinical practice
HBsAg	hepatitis B surface antigen
HBV DNA	hepatitis B Virus deoxyribonucleic acid
HCV RNA	hepatitis C virus ribonucleic acid
HDPE	high-density polyethylene
HIV	human immunodeficiency virus
HIV RNA	human immunodeficiency virus ribonucleic acid
IB	investigator's brochure
IBD	inflammatory bowel disease
ICF	informed consent form
ICH	International Conference on Harmonization
ICU	intensive care unit
IgM	immunoglobulin M
IL-1	interleukin-1
IL-1 β	interleukin-1beta
IL-6	interleukin-6
IND	investigational new drug
INR	international normalized ratio
IRB	institutional review board
ISF	investigator site file
ITT	intention to treat
IU/L	international units per liter
IV	intravenous
LTSE	long term safety extension
MAP	mean arterial pressure
MCP1	monocyte chemoattractant protein-1
MELD	model for end stage liver disease
mg	milligram(s)

mL	milliliter(s)
mm Hg	millimeter of mercury
mmol/l	millimoles per liter
NAFLD	nonalcoholic fatty liver disease
NASH	nonalcoholic steatohepatitis
NDB	nutrition database
NIAAA	National Institute on Alcohol Abuse and Alcoholism
NIH	National Institute of Health
PBC	primary biliary cirrhosis
PI	principal investigator
PLB	placebo
PK	pharmacokinetic(s)
PROMIS	patient reported outcomes measurement system
qSOFA	quick-sequential organ failure assessment
SAE	serious adverse event
SIRS	systemic inflammatory response syndrome
SOC	standard of care
SOFA	sequential organ failure assessment
SUSAR	suspected, unexpected serious adverse reaction
SAP	statistical analysis plan
TEAE(s)	treatment-emergent adverse event(s)
TIPS	transjugular intrahepatic portosystemic shunt
TNF- α	tumor necrosis factor-alpha
TNF- β	tumor necrosis factor-beta
UA	urinary analysis
UDCA	ursodeoxycholic acid
U/L	units per liter
ULN	upper limit(s) of normal
US	United States (of America)
vs	versus
WBC	white blood cell
WIRB	Western Institutional Review Board

